### 3. OBJECTIVES AND ENDPOINTS

#### 3.1. Primary objective:

*Primary objective 1:*

- To evaluate the safety and tolerability of VRC01/VRC01LS mAb administered through IV infusion.

*Primary endpoints 1:*

- Local and systemic reactogenicity, laboratory measures of safety, AEs, SAEs, and rates of discontinuation.

*Primary objective 2:*

- For each sex at birth, to evaluate the pharmacokinetics of VRC01 in serum versus mucosa in each mucosal compartment.

*Primary endpoint 2 (Groups 1 & 2 & 4):*

- Serum concentration of VRC01 out to Month 6 after the last infusion.
- Levels of VRC01 in genital and rectal secretions, as well as cervical, vaginal, and rectal tissues at the collection timepoints.

#### 3.2. Secondary objective:

*Secondary objective 1:*

- To evaluate the ability of the *in vivo*-infused VRC01/VRC01LS antibodies to inhibit HIV-1 infection in tissue explants.

*Secondary endpoint 1:*

- *Ex vivo* inhibition of HIV-1 infectivity in tissue biopsies in Groups 1 – 3.

#### 3.3. Exploratory objectives and endpoints

*Exploratory objective 1:*

- For each sex at birth, to evaluate the pharmacokinetics of VRC01LS in serum versus mucosa in each mucosal compartment.

*Exploratory objective 2:*

- To evaluate the levels of VRC01LS in serum, mucosal secretions, and mucosal tissues and those of VRC01 at the 30 mg/kg dose level.

*Exploratory objective 3:*

- To evaluate the tissue distribution of VRC01/VRC01LS in mucosal biopsies.

*Exploratory objective 4:*

- To compare the levels and functionality of VRC01/VRC01LS in mucosal secretions and tissues between the cervical, vaginal, and rectal compartments from the same participant.

*Exploratory objective 5:*

- To assess the relationship between inflammation in mucosal biopsies and levels of antibody in these tissues and related secretions.

*Exploratory objective 6:*

- To assess the acceptability and tolerability of repeat mucosal sampling, including secretions and biopsies, for application in future studies.

*Exploratory objective 7:*

- To assess the relationship between Fc receptor genotypes and VRC01/VRC01LS pharmacokinetics and/or ex vivo infectivity of biopsies.

*Exploratory objective 8:*

- To further evaluate the retention of functional characteristics of in vivo–infused VRC01/VRC01LS in each group, additional assays may be performed, including on samples from other timepoints.

*Exploratory objective 9:*

- To conduct analyses related to furthering the understanding of HIV, immunology, vaccines, antibody mediated prevention, and clinical trial conduct.

#### **4. COHORT DEFINITION**

##### **Participants**

79 healthy, HIV–uninfected adult volunteers aged 18 to 50 years, regardless of sex or gender

##### **Design**

Multicenter, randomized, placebo controlled, double-blind trial

##### **Duration per participant**

As VRC01LS is designed to have a longer half-life than VRC01, participants who receive VRC01 will be followed for 6 months after the last product administration and participants who receive VRC01LS will be followed for 12 months after the last product administration. Specifically,

Groups 1, 2, and 5: 12 months of scheduled clinic visits

Group 3: 18 months of scheduled clinic visits

Group 4: 6 months of scheduled clinic visits

##### **Estimated total study duration**

40 months (includes enrollment, and follow-up)

## 5. POTENTIAL CONFOUNDERS

Characterization of the safety of the vaccine is susceptible to confounding by adverse events not related to the vaccine that by chance occur more often in one arm of the trial than another. Therefore analyses involving adverse events will incorporate the reported relationship to product as assessed by HVTN staff.

## 6. RANDOMIZATION

The randomization sequence will be obtained by computer-generated random numbers and provided to each HVTN CRS through the SDMC via a Web-based randomization system. Participants will be randomized to either one of Groups 1-3 or one of Groups 4-5, depending on site. The randomization will be stratified by sex at birth and done in blocks to ensure balance across Groups 1-3, and across Groups 4 and 5. All participants will be randomized prior to the first infusion, ideally within 4 days. At each institution, the pharmacist with primary responsibility for dispensing study products is charged with maintaining consistency of the treatment assignments.

After the trial started, the enrollment was capped in Groups 3 and 5 at  $n=7$  and  $n=10$ , respectively in November 2017 and December 2017, to limit the number of VRC01LS participants due to the emerging of other more superior mAb products in the field.

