6.1 Accrual and sample size calculations

Recruitment will target enrolling approximately 74 healthy, HIV-uninfected adult participants into five groups receiving IV administration of either VRC01 or VRC01LS at different schedules and/or dose levels. Groups 1 and 2 participants receive 4 infusions of VRC01 every 2 months at the 10 mg/Kg and 30 mg/Kg dose levels, respectively; Group 3 participants receive 3 infusions of VRC01LS every 3 months at the 30 mg/Kg dose level; Groups 4 and 5 participants receive a single infusion of VRC01 or VRC01LS, respectively, at the 30mg/Kg dose level. Because Groups 1-3 will be enrolled at different sites from Groups 4 and 5, Groups 1-3 were originally randomized with a ratio of 1:1:1, stratified by sex at birth and, separately, Groups 4 and 5 were also originally randomized with a ratio of 1:1 stratified by sex at birth. Groups 3 and 5 will stop enrolling once a minimal number of 12 participants, regardless of sex at birth, are enrolled. At that point, Groups 1 and 2 will be randomized together with a ratio of 1:1, stratified by sex at birth. Groups 1 and 2 will still be enrolled at different sites from Group 4. Groups 1 and 2 (n=23/group) will now be randomized with a ratio of 1:1, stratified by sex at birth. A total of 10 male and 13 female participants will still be enrolled in each of Groups 1 and 2. In Groups 1-3, enrollment is concurrent with the first biopsy procedure(s). In Groups 4-5, enrollment is concurrent with the first infusion. For all groups, randomization occurs prior to the first infusion, ideally within 4 days.

All participants receiving the first complete or partial infusion will provide some safety data. However, for PK analyses of drug levels in serum and mucosa, it is possible that data may be missing for various reasons, such as participants terminating from the study early, or problems in obtaining or shipping specimens. For this reason, the sample size calculations in Section 6.1.2 account for 15% enrolled participants having missing data for the primary lab data endpoint.

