### Schema

Group	Treatment	Infusion schedule (Months)					
		N	M0	M2	M3	M4	M6
Group 1	VRC01 10 mg/kg	23	IV Infusion	IV Infusion		IV Infusion	IV Infusion
Group 2	VRC01 30 mg/kg	23	IV Infusion	IV Infusion		IV Infusion	IV Infusion
Group 3	VRC01LS 30 mg/kg	7*	IV Infusion		IV Infusion		IV Infusion
Group 4	VRC01 30 mg/kg	16	IV Infusion				
Group 5	VRC01LS 30 mg/kg	10*	IV Infusion				

\*Note: Groups 1, 2, and 3 will be randomized together. Groups 4 and 5 will be randomized together.

\*Note: enrollment has stopped in groups 3 & 5, no more participants will be enrolled to group 3 & 5

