For each tissue biopsy type, graphical and tabular summaries of the distributions of *ex vivo* inhibition of HIV-1 infectivity summarized by AUC (or other measurements) will be made for each challenge virus, treatment arm, and timepoint. Comparisons between groups 1-3 will be stratified by site. The difference between treatment arms at a specific timepoint will be tested with an extension of the nonparametric Wilcoxon rank sum test for two-way analysis (i.e., the Van Elteren test) if the data are not normally distributed and with a stratified 2-sample t-test if the data appear to be normally distributed. An appropriate data transformation may be applied to better satisfy assumptions of symmetry and homoscedasticity (constant variance). The same testing

approaches will be used to compare infectivity between male rectal vs. female cervical/vaginal, between male rectal vs. female rectal, and between female cervical vs. female vaginal at each time-point, stratified by dose groups.

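### In the SAP's tissue-infectivity comparisons of Group 3 (VRC01LS) with Groups 1 and 2, about 70% of each VRC01 arm is expected to have been randomized after Group 3 closed, and the plan neither counts nor labels these participants

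*SAP*

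**What the plan says.** Protocol 6.1 sets out two allocation phases. At first, "Groups 1-3 were originally randomized with a ratio of 1:1:1, stratified by sex at birth"; separately, "Groups 4 and 5 were also originally randomized with a ratio of 1:1 stratified by sex at birth". Once the VRC01LS arms stop: "At that point, Groups 1 and 2 will be randomized together with a ratio of 1:1, stratified by sex at birth". Protocol 6.2 adds that later participants are randomized to Group 1 or 2, or enrolled in Group 4, depending on site.

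SAP section 6 gives the caps: "After the trial started, the enrollment was capped in Groups 3 and 5 at" 7 (Group 3) and 10 (Group 5). It dates them "respectively in November 2017 and December 2017, to limit the number of VRC01LS participants". It still describes blocks balanced across Groups 1-3 and does not carry over the later two-arm scheme. One schema footnote still reads "Groups 1, 2, and 3 will be randomized together"; the next says that enrollment to Groups 3 and 5 has stopped.

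For the infectivity assay, SAP 8.5.2 tests treatment arms at each timepoint with a Van Elteren test or a stratified t-test: "Comparisons between groups 1-3 will be stratified by site". SAP 8.5.1 takes all enrolled participants by initial assignment. There is no enrollment-period stratum, concurrent subset or period sensitivity analysis. SAP section 5, on confounders, deals only with adverse events.

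**The concern.** A participant randomized after Group 3 closed had no chance of receiving VRC01LS. For that part of Groups 1 and 2, the contrast with Group 3 is not protected by randomization, and anything that changed over calendar time can enter the product difference.

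The infectivity assay is exposed to this because it runs on fresh tissue. SAP 8.5.2 has rectal explants challenged within 90 minutes of collection, and cervical and vaginal explants within 60 to 120 minutes. Early and late participants therefore cannot be run in one batch. Stratifying by site removes differences between the Seattle and Cape Town laboratories but not changes within a site over time.

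What is at stake is how the VRC01LS result may be described. Protocol 4.4 and 4.4.1 name a comparison of VRC01LS with VRC01 at 30 mg/kg as a purpose of the trial. The infectivity endpoint is secondary, and the primary VRC01 objectives do not depend on this contrast.

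**Working it through.** **Inputs.** Final sizes: 23, 23, 7, 16, 10 (SAP schema). Allocation 1:1:1 for Groups 1-3 and 1:1 for Groups 4-5 until closure (protocol 6.1). Planned sex split in Groups 1 and 2: 10 males and 13 females each (protocol 6.1). The documents give no count of VRC01 participants before and after closure, so the counts below are inferred.

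**Stated totals.** 23 + 23 + 7 + 16 + 10 = 79, as in the SAP. The protocol's figure of about 74 is 23 + 23 + 6 + 16 + 6.

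**Expected non-concurrent share.** Under 1:1:1, Groups 1 and 2 each hold about 7 when Group 3 reaches 7.
- Group 1 or Group 2 against Group 3: (23 − 7)/23 = 16/23 = 70%.
- Group 4 against Group 5, under 1:1: (16 − 10)/16 = 6/16 = 38%.

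**Sensitivity to blocking.** Block sizes are not stated. Permuted blocks were simulated with assumed sizes of 3, 6 or 9 and 2 or 4 strata. The number in Group 2 when Group 3 reached 7 had a median of 6 to 7, and the widest 95% range was 2 to 11. Even at 11, 12/23 = 52% of Group 2 is non-concurrent. More than half was non-concurrent in at least 99% of runs under every scheme.

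**Possible bias.** If later VRC01 participants differ by δ SD and nothing corrects for it, the all-participant contrast shifts by (16/23) × δ:

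| Assumed δ (SD) | Bias (SD) |
|---|---|
| 0.25 | 0.17 |
| 0.5 | 0.35 |
| 1.0 | 0.70 |

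The values of δ are assumptions; the documents report no drift.

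**Size of the contrasts actually planned.** SAP 10.1.1 tabulates arm comparisons by sex at birth, tissue and virus, so 7 v 23 is not a planned contrast. Assume that Group 3 has 3 males and 4 females. With SE = √(1/n₁ + 1/n₂) in SD units:

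| | All participants | Concurrent only |
|---|---|---|
| Males (rectal) | 3 v 10: 0.66 | 3 v 3: √(2/3) = 0.82 |
| Females (cervical, vaginal) | 4 v 13: 0.57 | 4 v 4: √(2/4) = 0.71 |

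**What a concurrent-only test could show.** The smallest two-sided exact rank p-value is 2/C(6,3) = 2/20 = 0.10 at 3 v 3. At 4 v 4 split 2 + 2 over two sites it is 2/(6 × 6) = 0.056. An estimate with an interval is usable; a test is not.

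**The case against.** The strongest reply is that the SAP already has safeguards. All Group 1-3 participants are scheduled for baseline biopsies challenged in the same assay (protocol Table 9-1). SAP 10.1.1 tables arm comparisons at baseline and on baseline-subtracted AUC. A lasting shift in assay, virus stock or population would show at baseline and largely cancel on subtraction. TLA staff are blinded to group (SAP section 7). This stands in part. Adjustment applies only if the baseline correlation exceeds 0.5 with p < 0.05, and change between baseline and Month 6 or later would remain. The bias figures above are therefore what could occur without correction.

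Four stronger readings are tempting, and the documents do not support them.

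- *That every VRC01LS comparison is affected, and mostly non-concurrent.* The only specified test is TLA infectivity in Groups 1-3. Mucosal and serum levels get summaries and plots. Group 5 against Group 4 has no infectivity endpoint and no specified test, and is about 38% non-concurrent.
- *That the protocol lets this assay be updated mid-study.* That wording is in 10.3.1 (drug levels, where any assay must first be qualified) and 10.3.2 (immunohistochemistry). Section 10.4.1, on infectivity, has no such sentence.
- *That the SAP conceals the closure.* Section 6 gives both caps and dates, the schema says that enrollment stopped, and 8.5.1 says that small samples limit inference. What is missing is the revised allocation and its consequence for the contrast.
- *That a product difference should be believed only if the full and concurrent estimates agree in sign.* The concurrent set lies inside the full set, so the two agree often whatever the truth. At 3 v 10 with no true effect, simulated agreement is 80% without drift and 74% with 0.5 SD drift. With a true 0.5 SD effect and no drift, they still disagree 16% of the time.

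**Conclusion.** The point holds for the TLA comparisons of Group 3 with Groups 1 and 2. About 70% of each VRC01 arm is expected to be non-concurrent, and a majority is very likely under any blocking scheme tried. The plan does not identify this or account for it. The share rests on 1:1:1 allocation up to closure at 7; the sponsor's randomization dates will give the exact figure. The effect on the result is unknown: possible confounding is reduced, not removed, by the baseline data. The conclusion limits how the secondary contrast may be described. It does not show that the contrast is biased, and it leaves the primary VRC01 objectives untouched.

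**What to change.** In SAP 8.5.2, for each TLA contrast involving Group 3:

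1. Report how many VRC01 participants were randomized before and after Group 3 closed. Use the randomization date, because Groups 1-3 enroll at the baseline biopsy, before randomization.
2. Label the all-participant contrast as including non-concurrent controls.
3. Report beside it an estimate with confidence interval limited to participants randomized while Group 3 was open, by tissue and sex, stratified by site where cells allow. Describe it as supportive and not as a powered test, and attach no sign-agreement rule.

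Apply the same labelling to any descriptive Group 5 against Group 4 display (about 6 of 16 non-concurrent). Bring the SAP schema note and section 6 into line with the revised allocation in protocol 6.1 and 6.2.

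The cost is SAP wording and one rerun per contrast from dates already held. The all-participant analysis keeps its full precision. The drawback is that the added estimate is weak: its standard error is about 24% larger than that of the matching full contrast (0.82 against 0.66; 0.71 against 0.57), and some site-by-sex cells may be empty.

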## 7. BLINDING

The study will be open label. Lab staff performing the TLA and Singulex assays will be blinded to group assignments for all groups; lab staff performing the ELISA assay measuring mAb concentrations in serum will be unblinded to assignments to VRC01 or VRC01LS groups.

## 8. STATISTICAL ANALYSIS

This section describes the final study analysis. Of note, Groups 1-3 participants are enrolled 1 month before the first infusion. Groups 4 and 5 participants are enrolled at the first infusion. All analyses pertaining to the safety and drug level objectives of this study are intent-to-treat analyses that include all randomized individuals per their randomization allocation. In addition, analyses will also be performed as treated accounting for the actual infusions and dose levels each participant received.

No formal multiple comparison adjustments will be employed for multiple safety endpoints.

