7.3.6 Participant termination from the study

Under certain circumstances, an individual participant may be terminated from participation in this study. Specific events that will result in early termination include:

- Participant refuses further participation,
- Participant relocates and remote follow-up or transfer to another HVTN CRS is not possible,
- HVTN CRS determines that the participant is lost to follow-up, or
- Investigator decides, in consultation with Protocol Team leadership, to terminate participation (eg, if participant exhibits inappropriate behavior toward clinic staff).
- Any condition where termination from the study is required by applicable regulations.
- Participant declines further mucosal biopsies between the baseline biopsies and the first infusion (Groups 1-3).

If study product is not detectable in any of the samples (including biopsies) at two consecutive follow-up visits, participants may be excluded from further sample collections at the discretion of the HVTN 116 PSRT. If such a decision is reached, the participant will be terminated after a final study visit.

8 Study product preparation and administration

CRS pharmacists should consult the Pharmacy Guidelines and Instructions for DAIDS Clinical Trials Networks for standard pharmacy operations. The protocol schema is shown in [Table 3-1](#).

See the Investigator's Brochures for further information about study products.

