9.3 Enrollment visits

Enrollment in Groups 1, 2, and 3 is simultaneous with baseline biopsy collections on day -14. Enrollment in Groups 4 and 5 is simultaneous with the infusion on day 0. The time interval between randomization and first infusion should not exceed 4 working days. The CRS requests the randomization assignment from the Web-based randomization system. Randomization will be performed prior to first infusion for all groups.

At the baseline biopsy collection visit (Groups 1-3; day -14), cervical, vaginal, and/or rectal biopsies will be collected. These samples will serve as baseline controls and will help to assess the acceptability of the biopsy procedures to participants and the fitness of participants to continue in these groups with extensive mucosal biopsy collections. Participants with conditions not amenable to repeated biopsy sampling or participants not willing to continue in the trial after these baseline biopsies have been performed may be replaced.

At the baseline biopsy collection visit (Groups 1-3; day -14), the following procedures are performed:

- Abbreviated physical examination, including weight, vital signs, and a symptom-directed evaluation by history and/or appropriate physical exam based on participant self-reported symptoms or complaints
- Assessment of concomitant medications (Section 9.2)
- Assessment of any new or unresolved AEs/intercurrent illnesses
- Urine or serum pregnancy test (for participants who were born female). Persons who are NOT of reproductive potential due to having undergone bilateral oophorectomy (verified by medical records), are not required to undergo pregnancy testing
- Risk reduction counseling (Section 9.7)
- Pregnancy prevention assessment (Section 9.2 and 9.8)

- Assessment of new or unresolved social impacts (site staff will ask participant about the status of any unresolved social impacts and if s/he has experienced any new social impacts as a result of the trial participation)
- Specimen collection (including mucosal sampling as described in Section 9.6);
- HSV 1/2 testing
- Blood hormone levels (estradiol and progesterone) (persons born female only)
- Confirm that participants received HIV test results from previous visit. If not, provide test results and post-test counseling as appropriate.

For the enrollment infusion visit (Groups 4 and 5; day 0) procedures are described in Section 9.4.

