## 9. SAFETY TABLES AND FIGURES

### 9.1 List of Tables

- Enrollment Report
- Demographics and Study Product Administration Frequencies
- Overall Protocol Status
- Maximum Local and Systemic Reactogenicity Summaries
- Adverse Experiences by Body System and Severity – By Decreasing Frequency
- Adverse Experiences by Preferred Term and Severity – By Decreasing Frequency – Includes Severe, Life-threatening or Fatal Events Only
- Adverse Experiences by Preferred Term and Severity – By Decreasing Frequency – Includes Events of All Severities
- Adverse Experiences by Preferred Term and Relationship to Study Product – By Decreasing Frequency – Includes Related Events Only
- Adverse Experiences by Preferred Term and Relationship to Study Product – By Decreasing Frequency – Includes Events of Any Relationship
- Adverse Experiences by Preferred Term and Relationship to Mucosal Sampling – By Decreasing Frequency – Includes Related Events Only
- Adverse Experiences by Preferred Term and Relationship to Mucosal Sampling – By Decreasing Frequency – Includes Events of Any Relationship
- Expedited Adverse Experiences (EAEs) Reported to the Regulatory Support Center (RSC)
- Pregnancy Listing
- Social Impact Summary
- End of Study Diagnostic ELISA Testing Results
- Local Lab Value Summary Statistics

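### Groups 1-3 participants who leave between the day -14 biopsies and randomization fall outside the by-arm tables of mucosal-sampling AEs and early termination

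*SAP*

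**What the plan says.** **Timing.** Protocol section 9.3: "Enrollment in Groups 1, 2, and 3 is simultaneous with baseline biopsy collections on day -14". Randomization comes later. The same section states: "The time interval between randomization and first infusion should not exceed 4 working days". SAP section 6 states: "All participants will be randomized prior to the first infusion, ideally within 4 days". Appendix L marks randomization for Groups 1 and 2 at visit 3, day 0, and Appendix M does the same for Group 3.

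**Exit and replacement.** Protocol section 9.3 uses the baseline biopsies partly to see whether participants accept the procedure and are fit to go on. Those with conditions unsuited to repeat sampling, and "participants not willing to continue in the trial after these baseline biopsies have been performed may be replaced". Protocol section 7.3.6 lists as a reason for early termination: "Participant declines further mucosal biopsies between the baseline biopsies and the first infusion (Groups 1-3".

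**Analysis set.** SAP section 8 (same text in protocol section 6.4) says that the safety analyses are "intent-to-treat analyses that include all randomized individuals per their randomization allocation". An as-treated analysis is added, defined by the infusions and doses actually received. SAP section 8.4 says only that anyone given any infusion, even an incomplete one, contributes safety data.

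**Tables.** SAP section 8.4.2 tabulates AEs by treatment arm, including by relationship to mucosal sampling. SAP section 9.1 lists two outputs titled "Adverse Experiences by Preferred Term and Relationship to Mucosal Sampling", one for related events and one for all events. SAP section 8.4.4 tabulates early termination by reason and arm.

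**The concern.** Exposure to biopsy starts at enrollment, whereas the analysis set starts at randomization. The gap is about two weeks on the protocol's schedule, and the exit rules for it concern willingness and fitness to undergo further biopsies. The all-randomized rule therefore selects on something close to the outcome that the sampling-AE and early-termination tables are meant to describe. The as-treated analysis does not recover these people, because they received no infusion.

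This matters because protocol section 11.2.2 defines an AE to include events associated with study procedures, and the SAP adds relationship to mucosal sampling to the AE summaries, which protocol section 6.4.3.2 does not mention. A reader planning a later biopsy study will take these tables as the rate among people offered biopsies. For Groups 1-3 they give the rate among people who remained after the first round.

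The arms also differ. Groups 4 and 5 have their first biopsy at visit 4 (protocol Table 9-2), after randomization and infusion. A participant there who tolerates biopsy badly stays in the table, while a similar participant in Groups 1-3 can leave before entering it.

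**Working it through.** **1. Can a biopsied participant be outside every defined safety set?** Take someone in Groups 1-3 who has the day -14 biopsies, declines more, and leaves before randomization.
- All-randomized set (SAP 8): not included.
- As-treated analysis (SAP 8): no infusion, not included.
- Any-infusion statement (SAP 8.4): not included.
- By-arm AE and termination tables (SAP 8.4.2, 8.4.4): no arm, hence no column.

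Someone who leaves after randomization but before infusion stays in the intent-to-treat set. The gap is limited to exits before randomization.

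**2. Do the plan's own safety figures reproduce?** Yes, and the concern disputes none of them. For n = 23, the true rate giving a 90% chance of at least one event is 1 - 0.1^(1/23) = 9.53%, against 9.52% in protocol section 6.1.1. The score upper bound for 0/n is 3.84/(n + 3.84). For 0/23 it is 3.84/26.84 = 14.3%, against 14.31% stated.

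**3. How large could the effect be?** Inputs:
- Randomized in Groups 1-3: 23 + 23 + 7 = 53 (SAP section 2 schema, taken as randomized counts).
- Leavers before randomization: k, not in the documents; assumed 1 to 10.
- Share of leavers with a sampling-related AE: q, not in the documents; taken from 0 to 1.
- Randomized participants with a sampling-related AE: x; 0 and 3 are used as examples.

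Exits missed by the by-arm termination table, as a share of those biopsied = k/(53 + k).
Sampling-AE rate among all biopsied = (x + qk)/(53 + k).

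| k | Missed exits | Rate if 0/53 reported, q from 0 to 1 | Rate if 3/53 = 5.7% reported, q from 0 to 1 |
|---|---|---|---|
| 1 | 1/54 = 1.9% | 0 to 1.9% | 5.6% to 7.4% |
| 3 | 3/56 = 5.4% | 0 to 5.4% | 5.4% to 10.7% |
| 5 | 5/58 = 8.6% | 0 to 8.6% | 5.2% to 13.8% |
| 10 | 10/63 = 15.9% | 0 to 15.9% | 4.8% to 20.6% |

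For scale, the score upper bound for 0/53 is 3.84/56.84 = 6.8%. With q = 1, three leavers (5.4%) stay inside that bound and five (8.6%) fall outside it.

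**4. Direction.** The early-termination rate is understated whenever k is at least 1, because every leaver is a termination. For sampling AEs the direction depends on q. If leavers had no AEs, the rate falls slightly (3/53 = 5.7% becomes 3/63 = 4.8% at k = 10). Since exit is linked to unfitness or unwillingness for biopsy, understatement is the likelier direction, but the documents do not settle it.

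**The case against.** Several points on the other side stand and limit the concern.

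- **Replacement is optional.** Protocol section 9.3 says may. The section 7.3.6 window runs to the first infusion, so some exits under it happen after randomization and stay in the analysis.
- **Leavers need not disappear from all reporting.** SAP section 9.1 lists an Enrollment Report and an Overall Protocol Status table. Neither is stated to be limited to randomized participants, though neither is stated to include leavers.
- **Not all sampling-AE data are selected.** Groups 4 and 5, 16 + 10 = 26 of 79 participants, have no biopsy run-in and have their own columns.
- **The size is assumed.** Unwillingness to continue is not itself an AE, and the background in protocol section 4.8 is reassuring: grade 1 events in 1.5% to 4.6% of 65 volunteers in one rectal biopsy study, and no complications in two series of more than 150 and more than 160 biopsy visits.

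A reader might also infer that the acceptability results are biased. SAP section 3.3 does include the objective "To assess the acceptability and tolerability of repeat mucosal sampling, including secretions and biopsies, for application in future studies", but the documents do not support that inference. The all-randomized rule covers the safety and drug-level objectives, and SAP sections 9 and 10 list no acceptability output and set no population for one. The first acceptability questionnaire is at visit 3, and at early termination protocol section 9.12 only asks staff to consider one.

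Nor does the gap bias the comparison of product safety between arms or the drug-level endpoints, since these exits precede allocation.

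None of this fills the gap in the two sampling-AE tables and the early-termination table. The SAE listing does not clearly fill it either: it covers events reported to the DAIDS safety office, and the reporting period in protocol section 11.2.3 starts at first product administration.

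**Conclusion.** The concern holds in a limited form. Followed as written, the plan leaves Groups 1-3 participants who exit between the baseline biopsies and randomization out of the by-arm tables of sampling-related AEs and early termination. Any such exit understates Groups 1-3 dropout. Their sampling-AE rate is likely understated too, and neither rate is directly comparable with Groups 4-5.

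The size cannot be fixed from the documents. It rests on 53 randomized, an assumed 1 to 10 leavers, and an unknown share of leavers with an AE. Under those assumptions, missed dropout is 1.9% to 15.9% of those biopsied, and a reported 0/53 could correspond to 0% to 15.9%. If no one left before randomization, there is no effect. The primary product-safety and drug-level conclusions do not depend on this point. The change is still worth making, because the stated set selects on what these tables report and the remedy is cheap.

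**What to change.** 1. Define an additional set: all enrolled participants with at least one biopsy, randomized or not. Use it for the two mucosal-sampling AE tables and the early-termination table, with an *enrolled, not randomized* column for Groups 1-3.
2. Report how many Groups 1-3 participants left before randomization, why, and how many were replaced.
3. Keep the randomized and as-treated sets for product-related tables.
4. If an acceptability summary is produced, state that leavers may have no questionnaire.
5. Reconcile SAP section 8 and protocol section 6.4, which put Groups 1-3 enrollment one month before the first infusion, with protocol section 9.3, which puts it at day -14. The length of the uncovered window depends on this.

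The cost is one set definition, one column and a short disposition summary, with no new visits. The limitation is incomplete data. AEs are assessed from visit 2 (Appendices L and M), but visit 2 is the biopsy visit itself and the next scheduled AE assessment is visit 3. AE follow-up for leavers may therefore be partial, and the column should carry a note saying so.
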